4. Number of NMO/NMOSD-related in-patient hospitalizations. In-patient hospitalization is defined as more than an overnight stay.
5. Annualized attack rate (total number of AC-determined NMO/NMOSD attacks normalized by person-years-) during any exposure to MEDI-551.
6. Treatment-emergent adverse events (TEAEs), including treatment-emergent serious adverse events (TESAEs). Laboratory measurements as well as their changes or shift from baseline over time.
7. Pharmacokinetic profile of MEDI-551.
8. Incidence of anti-drug antibodies (ADAs) directed against MEDI-551 for the duration of the study, both predose and postdose for each subject.

Exploratory Endpoints:

1. Change from baseline in the 4-week recall SF-36 PCS and MCS at the last visit during the RCP.
2. Change from baseline in pain NRS in 5 locations at the last visit during the RCP.
3. B-cell counts (total and subsets).
4. Change from baseline in plasma cell gene signature.
5. Serum AQP4-IgG titers.

STUDY DESIGN

This is a multicenter, multinational, randomized, double-masked, placebo-controlled- study with an open-label extension period to evaluate the efficacy and safety of intravenous (IV) MEDI-551 in adult subjects with AQP4-IgG seropositive and seronegative NMO and NMOSD. Enrollment of subjects into the study will stop when a total of 67 AC-determined NMOSD attacks have occurred, when 252 subjects have been randomized and dosed, or following a recommendation by the independent Data Monitoring Committee (DMC) to stop enrollment, whichever occurs first. Following a screening period of up to 28 days, subjects will be randomized in a 3:1 ratio to receive IV MEDI-551 (300 mg at Day 1 and 300 mg at Day 15) or placebo for a period of 197 days (RCP).

Subjects who complete the RCP without experiencing an NMO/NMOSD attack will be given the option to enroll into an OLP and will initiate or continue treatment with MEDI-551. Subjects who experience an AC-determined NMO/NMOSD attack during the RCP will be given the option to enroll- into the OLP following

rescue therapy. Subjects for whom the NMO/NMOSD attack is not determined by the AC will continue in the RCP until Day 197 (or until another attack occurs that is determined by the AC).

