4.3.1.5 Independent Adjudication Committee

Three experts in NMO/NMOSD disease will constitute the independent AC. This committee has the mandate to evaluate each data set that is generated during the Assessment Visit and determine if an NMO/NMOSD attack occurred based on the clinical presentation, assessments, and the protocol-defined criteria for an NMO/NMOSD attack. The committee is completely independent and blinded to treatment assignments and/or to pertinent treatment

unmasking information (eg, B-cell counts, AQP4-IgG titers post-randomization) of study subjects, and to any decision made by the Principal Investigator regarding an NMO/NMOSD attack. The committee will use its judgement and clinical experience to make its determination based on the data provided. The committee will review the same data that are available to the Principal Investigator when he/she makes his/her determination about the attack. In exceptional cases, determined and justified by the committee as such, the committee can request to review additional data that is essential to make a determination. The committee's role, function and procedures are governed by a separate charter.

The data from all subjects who are assessed at an Assessment Visit due to a new symptom(s) or worsening of an existing symptom(s) related to NMO/NMOSD will be sent for adjudication by the AC regardless of whether the Principal Investigator has determined that an NMO/NMOSD attack has occurred. Furthermore, the AC will not receive information about which protocol attack criterion was met and the rescue medication utilized.

Determination of an NMO/NMOSD attack by the AC is for the purpose of determining which events will be included in the primary analysis. It will NOT affect the rescue therapy that a subject may receive.

Only subjects in whom the attack was determined by the AC will be given the option to enter the OLP.

In addition, the data set that was generated and used by the Principal Investigator to assess the symptom(s) that were determined not to be related to NMO/NMOSD in the RCP, will be delivered to the AC for a non-real-time review.

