6 INTER AND INTRARATER RELIABILITY

A study will be conducted to establish inter- and intrarater reliability of the AC members. A random sample of 50% of AC determinations (separately for attack and non-attack) during the RCP will be selected for this purpose. For individual subject thus selected individual rater decision for both original assessment and reassessment time point will be included for this analysis. The intraclass correlation coefficient (ICC) for both inter- and intrarater reliability will be assessed by a random effects model ([Vangeneugden et al.](#)) based on the binary response (attack vs non-attack). The source of individual random effects will be attributed to subject, rater, and time (original vs reassessment). A joint random effect of rater and time will also be included to account for any excess variability. The corresponding statistical model is described below:

$$Y_{prd} = \frac{\exp(\alpha + b_p + b_r + b_d + b_{rd})}{1 + \exp(\alpha + b_p + b_r + b_d + b_{rd})} + \varepsilon_{prd}$$

where b_p, b_r, b_d and b_{rd} are the independent random effects due to subject, rater, time and joint random effect of rater and time distributed as normal with zero mean and variances $\sigma_p^2, \sigma_r^2, \sigma_d^2$ and σ_{rd}^2 respectively. Also ε_{prd} represents an error term normally distributed (independent of other random effects) with mean zero and variance σ_e^2 . The intraclass correlation coefficients are defined as follows:

$$ICC_{\text{Intra}} = \frac{\sigma_p^2 + \sigma_r^2}{\sigma_p^2 + \sigma_r^2 + \sigma_d^2 + \sigma_{rd}^2 + \sigma_e^2} \quad \text{and} \quad ICC_{\text{Inter}} = \frac{\sigma_p^2 + \sigma_d^2}{\sigma_p^2 + \sigma_r^2 + \sigma_d^2 + \sigma_{rd}^2 + \sigma_e^2}$$

The CIs of the ICCs will be calculated based on the method outlined in [Carrasco et al.](#) The standard error of the ICC is obtained by using the delta method:

$$V(\text{ICC}) = \mathbf{d}'\Sigma\mathbf{d}$$

where \mathbf{d} represents the derivatives of ICC with respect to their components denoted by the vector $\boldsymbol{\theta} = (\sigma_p^2, \sigma_r^2, \sigma_d^2, \sigma_{rd}^2, \sigma_e^2)$, $\mathbf{d} = \frac{d}{d\boldsymbol{\theta}}(\text{ICC})$ and Σ is the variance–covariance matrix of the $\boldsymbol{\theta}$. Let, $V_{\text{tot}} = \sigma_p^2 + \sigma_r^2 + \sigma_d^2 + \sigma_{rd}^2 + \sigma_e^2$, then \mathbf{d} will be defined by the following quantities:

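### SAP Section 6 models adjudicator reliability without a determination-by-rater effect and indexes cases by subject, so both ICCs can be biased if members differ consistently on cases or subjects recur

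*SAP*

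**What the plan says.** SAP Section 6 draws its sample from committee decisions: "A random sample of 50% of AC determinations (separately for attack and non-attack) during the RCP will be selected for this purpose". The next sentence changes the unit: "For individual subject thus selected individual rater decision for both original assessment and reassessment time point will be included for this analysis". The outcome is each member's yes/no decision, "based on the binary response (attack vs non-attack".

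The random effects are introduced as follows: "The source of individual random effects will be attributed to subject, rater, and time (original vs reassessment". One interaction is added: "A joint random effect of rater and time will also be included to account for any excess variability". Under the model equation, the terms "are the independent random effects due to subject, rater, time and joint random effect of rater and time", and an error term completes the list. The response therefore carries three indices: subject (p), rater (r) and time (d). The printed formulas are

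- `ICC_Intra = (σp² + σr²)/V_tot`
- `ICC_Inter = (σp² + σd²)/V_tot`
- `V_tot = σp² + σr² + σd² + σrd² + σe²`

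Protocol Section 4.3.1.5 fixes the number of raters: "Three experts in NMO/NMOSD disease will constitute the independent AC". It has them judge each Assessment Visit data set. Under the Protocol Synopsis (Study Design), a subject whose event the AC does not accept as an attack "will continue in the RCP until Day 197 (or until another attack occurs that is determined by the AC".

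**The concern.** The design is paired, because one member reads one case twice, and crossed, because three members read that case. A re-read tends to match a member's own first read better than a colleague's read when that member sees the case consistently differently from colleagues. That is a case-by-rater effect, and the model has none. The rater-by-time term cannot replace it, because it does not vary from case to case.

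The second mismatch is the unit. A subject can have a non-attack determination and later an attack determination, and both can be sampled. With only a subject index, the model takes these as repeat ratings of one thing, so a correct no for one event and a correct yes for another count as disagreement.

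The primary endpoint is the AC's determination, and this analysis is meant to show how reproducible those determinations are. If it is mis-specified, the report could say that members agree with themselves hardly better than with colleagues when that is false. The confidence intervals use the same variance components.

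**Working it through.** **No figure to reproduce.** The SAP gives no ICC value, target or variance component. Its printed derivatives were checked numerically and are correct for its own formulas. The problem lies in the model, not in the algebra that follows it.

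**1. What the printed gap can contain.** Subtracting the two formulas gives

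`ICC_Intra − ICC_Inter = (σr² − σd²)/V_tot`

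Only average leniency and average time shift appear. If both are near zero, the two ICCs coincide however faithfully members repeat their case decisions. If `σd² > σr²`, the intra value falls below the inter value.

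**2. Where an omitted case-by-rater variance goes.** Write it as `σer²`. For n cases, 3 raters and 2 reads, a variance-component fit has these expected mean squares:

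- Cases: `6σp² + 2σer² + σe²`
- Case by rater, 2(n−1) df: `2σer² + σe²`
- Remaining residual, 3(n−1) df: `σe²`

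Without the term, the last two lines are pooled over 5(n−1) df:

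- Fitted error: `σe² + (2/5)(2σer²) = σe² + 0.8σer²`
- Fitted case variance: `σp² + (2σer² − 0.8σer²)/6 = σp² + 0.2σer²`

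Total variance is unchanged. With share = `σer²/V_tot`, ICC_Intra falls by 0.8 × share and ICC_Inter rises by 0.2 × share. Assuming `σp²` = 0.6 of the total and `σr² = σd² = 0`:

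| Assumed share | True intra | True inter | Fitted, both |
|---|---|---|---|
| 0.1 | 0.70 | 0.60 | 0.62 |
| 0.2 | 0.80 | 0.60 | 0.64 |
| 0.3 | 0.90 | 0.60 | 0.66 |

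**3. Binary decisions, two choices of residual.** Yes/no decisions were simulated for 60,000 cases with assumed logit variances, and a case-only logistic model was fitted. The fitted case variance was 9.56 for (case 20, case-by-rater 5) and 4.35 for (20, 20).

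With a latent logit residual (π²/3 = 3.29):

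- (20, 5): fitted 9.56/12.85 = 0.744 for both, against true intra 25/28.29 = 0.884 and inter 20/28.29 = 0.707.
- (20, 20): fitted 4.35/7.64 = 0.569 for both, against true intra 40/43.29 = 0.924 and inter 20/43.29 = 0.462.

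As printed, the error is added to a fitted probability while the other variances are on the logit scale. Taking the error variance as the mean of p(1−p):

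- (20, 5): printed model 9.56/(9.56 + 0.112) = 0.988 for both. With the term, intra is 25/25.075 = 0.997 and inter 20/25.075 = 0.798.
- (20, 20): printed model 4.35/(4.35 + 0.148) = 0.967 for both. With the term, intra is 40/40.061 = 0.998 and inter 20/40.061 = 0.499.

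The direction is the same on both scales. On the printed scale, intra loses 1 to 3 points, while inter is inflated by 19 to 47 points.

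**4. Subject instead of determination.** Let q be the share of sampled subjects who contribute two determinations, and ρ the correlation between those two case effects. The expected within-subject sum of squares is `5σe²` for one determination and `11σe² + 6σp²(1−ρ)` for two. Pooling over 5 + 6q df per subject, the error gains

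`σp²(1−ρ) × 6q/(5 + 6q)`

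and the case variance loses the same amount. For an assumed true ICC of 0.80 (intra = inter):

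- q = 0.1: 0.80 × (1 − 0.6/5.6) = 0.71 at ρ = 0, and 0.74 at ρ = 0.3.
- q = 0.2: 0.80 × (1 − 1.2/6.2) = 0.65 at ρ = 0, and 0.69 at ρ = 0.3.

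Simulation gave 0.72, 0.74, 0.64 and 0.69. Both ICCs fall together.

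**5. How large q can be.** If a fraction f of adjudicated subjects have two determinations and half of all determinations are drawn, then `q = 0.25f/[0.5(1−f) + 0.75f] = f/(2+f)`. So q = 0.1 needs f = 22%, q = 0.2 needs f = 50%, and with at most two each q cannot exceed 1/3. At f = 10%, q = 0.048 and the 0.80 becomes 0.80 × (1 − 0.286/5.286) = 0.76.

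**The case against.** Several points against the concern stand.

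- **Size.** The documents give no variance components and no count of repeat determinations. A reader might infer that intra-rater reliability will certainly be understated. The text does not support that: with zero case-by-rater variance and one determination per subject there is no bias.
- **Scale.** A reader might carry the large latent-scale losses in ICC_Intra over to the printed formula. They do not carry over. On the printed scale the intra loss is small, and the printed value can even exceed the observed agreement.
- **Cause.** A reader might think that subject indexing also pulls the intra value toward the inter value. It does not; it lowers both. Only the missing interaction draws them together.
- **Wording.** The word subject in SAP Section 6 may be shorthand for the selected case. Protocol Section 4.8.7 samples only events that contribute to the primary analysis, where subject and event coincide. The unit problem comes from the SAP's wider sample, which includes non-attacks. Repeats also need an earlier non-attack, because an AC-determined attack ends the subject's RCP.
- **Importance.** A reader might take this as the trial's only evidence on adjudication quality. The SAP also plans an analysis of unanimous determinations, one restricted to clinical criteria (Section 3.4.1.4), AC–investigator agreement with kappa (Section 3.4.1.6), and a Cox model of investigator-determined attacks (Section 3.5.4). No threshold or decision rests on the ICCs.

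None of this supplies the missing term or an event index. The SAP uses cases as the denominator for AC–investigator concordance in Section 3.5.4, so the authors recognise that unit elsewhere.

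**Conclusion.** The point holds as a conditional, low-priority correction. The model cannot represent a member's case-specific self-consistency, which is what a paired re-read should reveal. If that component exists, a three-rater, two-read variance-component fit understates ICC_Intra by about 0.8 × share and overstates ICC_Inter by about 0.2 × share. An assumed share of 10% gives −8 and +2 points; 20% gives −16 and +4. Under the printed mixed-scale formula the sign is unchanged and the inflated ICC_Inter is the main fault.

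The subject index is a separate and probably smaller problem, which lowers both ICCs. Its size depends on how many subjects have two sampled determinations and how correlated those are. All the sizes given rest on assumed values. A reader might infer that the efficacy result is at risk; it is not, since these ICCs do not enter the primary Cox test.

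**What to change.** In SAP Section 6:

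- Index the case effect by AC determination, nested in subject if any subject contributes more than one.
- Add a determination-by-rater random effect with variance `σer²`.
- Include `σer²` in `V_tot` and in the ICC_Intra numerator: `ICC_Intra = (σcase² + σr² + σer²)/V_tot` and `ICC_Inter = (σcase² + σd²)/V_tot`.
- Add the matching element to θ and to the derivative vector d.
- Put the residual on the latent logit scale used by the other components. Without this, adding the term would still leave ICC_Intra near 1 in the examples above.

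The cost is SAP wording and one more variance component in the program; the planned ratings suffice. In simulation with an assumed 68 determinations the extra component was estimable, though intervals may be somewhat wider.

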Appendix 1 Sample Size Calculation

The proposed study is being planned to detect a target relative reduction of 60% in risk for time (days) from Day 1 to onset of an AC-determined NMO/NMOSD attack on or before Day 197 with 90% power and $\alpha = 0.05$ (two-sided), assuming an unequal randomization ratio of 3:1 to MEDI-551 versus placebo. Using the following formula, a total of 67 AC-determined NMO/NMOSD attacks will be required:

$$E = \left[\frac{z_{1-\alpha/2} + z_{1-\beta}}{\ln(HR)} \right]^2 \times \frac{(r+1)^2}{r},$$

where $z_{1-\alpha/2}$ and $z_{1-\beta}$ are $100(1 - \alpha/2)^{\text{th}}$ and $100(1 - \beta)^{\text{th}}$ percentile of a standard normal distribution, $r = 3$ is the randomization ratio and $HR = \text{hazard ratio} = 0.4$.

Following the completion of the first 78 subjects in this study the sample size was reviewed. The attack rate of the first 78 subjects to complete the RCP was used to simulate the remaining subjects to estimate the probability of reaching the required 67 AC-determined attacks. The simulation showed that with a sample size of 252 subjects there is a 90% probability of reaching the required 67 AC-determined attacks.

The remaining text in this appendix describes the process of defining the original sample size of 212 subjects.

Assuming hazard rates of 1.5/year and 1.0/year for an NMO/NMOSD attack in the placebo arm for seropositive and seronegative groups, respectively, and using the following formula:

$$N = \frac{E}{\Pr(\text{Fail})},$$

a total of 212 (with an upward adjustment) subjects are expected to be enrolled in this study where

$$\Pr(\text{Fail}) = s_1 P_1 + s_2 P_2$$

is the weighted average of the failure probabilities P_1 and P_2 in seropositive and seronegative cohorts, respectively, with associated stratum specific weights $s_1 = 0.8$ and $s_2 = 0.2$. Recall that subjects will be enrolled to seropositive and seronegative cohorts in 80:20 ratio.

Furthermore, the probability of an attack within i^{th} cohort ($i = 1, 2$) is given by

$$P_i = (1 - w)p_{i0} + wp_{i1}$$

the weighted average of the failure probabilities p_{i0} and p_{i1} for placebo and MEDI-551 groups, respectively; $p_{i0} = 1 - e^{-\lambda_{i0}F}$, $p_{i1} = 1 - e^{-\lambda_{i1}F}$; $F = 197/365 = 0.54$ to indicate the 197 days (28 weeks) duration of the controlled portion of the study; note that based on the

assumptions for this study, $\lambda_{10} = 1.5$, $\lambda_{11} = 0.6$, $\lambda_{20} = 1$ and $\lambda_{21} = 0.4$ and $w = \frac{r}{1+r} = 0.75$. Since the primary endpoint will be tested using the Cox proportional model, a simulation approach was used to investigate the power under alternative hypotheses mentioned above. Based on 5,000 simulations, the power for the overall and seropositive populations were observed as 94% and 91%, respectively. Moreover, the total required 67 events (212 subjects) were, on an average, distributed in seropositive and seronegative cohorts as 57 (168 subjects) and 10 (44 subjects) respectively.

The underlying hazard rate of time to an NMO/NMOSD attack in the seropositive placebo group is estimated based on a meta-analytic approach from several open-label cohort studies (see Table 7-1) in the absence of any placebo-controlled study in this population to date. These studies consisted of both seropositive and seronegative subjects and hence any finding related to hazard rate derived from these studies can be considered as an underestimation when applied for seropositive subgroup in the current study. Following are the 5 open-label studies considered with a total of 161 subjects:

Author	Title
Bedi et al	Impact of rituximab on relapse rate and disability in neuromyelitis optica. Mult Scler. 2011 Oct;17(10):1225-30
Costanzi et al	Costanzi C, Matiello M, Lucchinetti CF, Weinshenker BG, Pittock SJ, Mandrekar J, et al. Azathioprine: tolerability, efficacy, and predictors of benefit in neuromyelitis optica. Neurology. August 16, 2011;77(7):659-66.
Jacob et al	Treatment of neuromyelitis optica with rituximab: retrospective analysis of 25 patients. Muscle Nerve. 2008 Jan;39(1):87-90
Kim et al	Kim SH, Kim W, Li XF, Jung IJ, Kim HJ. Repeated treatment with rituximab based on the assessment of peripheral circulating memory B cells in patients with relapsing neuromyelitis optica over 2 years. Arch Neurol. 2011 Nov;68(11):1412-20.
Pittock et al	Pittock SJ, Lennon VA, McKeon A, Mandrekar J, Weinshenker BG, Lucchinetti CF, O'Toole O, Wingerchuk DM. Eculizumab in AQP4-IgG-positive relapsing neuromyelitis optica spectrum disorders: an open-label pilot study. Lancet Neurol. 2013 Jun;12(6):554-62.

The approximate time (months) between the first 2 pretreatment relapses was visually enumerated from the published figures for each study (Figure 7-1, Figure 7-2, Figure 7-3, Figure 7-4, and Figure 7-5). Subjects with second pretreatment relapses occurring within 12 months of the first relapse were considered failures. Hazard rate (assuming exponential distribution) was calculated from each study based on this failure rate. Overall hazard rate for time to second pretreatment relapse was calculated based on the weighted average of individual hazard rates (weight was based on number of failures from each study). The findings from this analysis are summarized in Table 7-2.

Table 7-2 Estimated Pretreatment Hazard Rate for Time to Relapse				
Study	Number of Subjects	No. of Subjects with Relapse by 1st Year	Percentage of Subjects Relapse Free by 1st Year	Hazard Rate (per year)
Bedi et al, 2011	23	14	39%	0.94
Costanzi et al, 2011	69	48	30.4%	1.2
Jacob et al, 2008	25	21	16%	1.83
Kim et al, Nov 2011	30	19	37%	0.99
Pittock et al, 2006	14	12	14.3%	1.94
Overall	161	114	29.2%	1.23

The weighted average of the hazard rates was determined as 1.33/year. As none of the cohorts in these studies received pure placebo treatment, the hazard rate for the placebo treatment for the seropositive subgroup in the current study is estimated to be 1.5/year. Conservatively, the hazard rate for the placebo treatment in seronegative subgroup is chosen as 1.0/year.

[figure not shown]

Figure 7-1 Neuromyelitis Optica Spectrum of Disorders Relapses Before and After Treatment with Azathioprine for 70 Patients with More Than 12 Months Follow Up

NMO = neuromyelitis optica.
Source: [Constanzi et al, 2011](#).

[figure not shown]

Figure 7-2 Attack Frequency Before, During, and After Eculizumab Treatment

Source: [Pittock et al, 2006](#).

[figure not shown]

Figure 7-3 Relapses in Patients with Neuromyelitis Optica Before and After Treatment with Rituximab

mo = months.

Source: [Jacob et al, 2008](#).

[figure not shown]

Figure 7-4 Disease Course of Patients Treated with Rituximab

Note: Disease course is depicted longitudinally, with each bar representing one patient. Each bar represents the type of treatment administered at a given time, a light gray bar representing no treatment, a dark gray representing other treatment (immunomodulatory, immunosuppressant) and black representing rituximab treatment. Each relapse is marked along the patient's course by a solid black or white mark. Time 0 on the X axis marks the initiation of rituximab treatment and divides pre- and post-rituximab treatment phases. Numbers on the X and Y axes represent months before/after rituximab initiation and patient number respectively. Most (17 of 23) patients had no recorded clinical relapses, and the remaining six had reduction in relapse frequency with rituximab treatment.

Source: [Bedi et al, 2011](#).

[figure not shown]

Figure 7-5 Relapses in Patients with Neuromyelitis Optica Before and After Treatment with Rituximab

mo = months.

Note: On the x-axis, 0 indicates start date of treatment. Each interrupted line on the y-axis represents a patient.

Source: [Kim et al, Nov 2011](#).

The target treatment effect of 60% has been estimated by comparing similar empirical evidence from [Costanzi et al, 2011](#) (treatment with azathioprine) and 3 articles from rituximab treatment ([Bedi et al, 2011](#), [Jacob et al, 2008](#), and [Kim et al, Nov 2011](#)). For each of these studies, the subjects who were relapse free within the first 12 months of respective treatment were visually identified (Table 7-3). Based on the survival rate thus obtained, the yearly constant hazard rate was calculated and the weighted average was determined.

Table 7-3 Calculated Yearly Constant Hazard Rate Based on Relapse-free Subjects in First 12 Months of Treatment

Study	N	No. of Subjects with Relapse by 1 st Year	Percentage of Subjects Relapse-free by 1 st Year	Hazard Rate (per year)
Bedi et al, 2011	23	4	83%	0.19
Jacob et al, 2008	25	7	72%	0.33
Kim et al, Nov 2011	30	6	80%	0.22
Overall	78	17	78%	0.25

The weighted average of the hazard for time to first relapse based on rituximab studies was determined as 0.258/year. Similarly, the hazard rate based on AZA treatment was calculated (Table 7-4). Based on this comparison, the relative reduction in risk of relapse was calculated as 57%.

Table 7-4 Relative Reduction in Risk of Relapse Based on Calculated Hazard Rate From Azathioprine and Rituximab NMO Studies					
Agent	N	Events Within 1st Year	Estimated Hazard Rate	Hazard Ratio	Relative Reduction in Risk of Relapse
Rituximab	78	17	0.25	0.43	57%
Azathioprine	70	31	0.58		
Total	148	48	N/A		

N/A = not applicable; NMO = neuromyelitis optica

Since the treatment effect from a placebo-controlled study is not available at this point, the 60% relative reduction in hazard rate was used as a conservative estimate for the target treatment effect. It is recognized that there are a number of caveats behind this approach; such as, the cohorts compared were not randomized and the selection of the patient population from each study may not be a true reflection of the currently proposed study.

